3.2 Participant Grouping

There are two treatment classes for the LTE and Integrated Analyses:

- **Group T-T** includes participants who were exposed to AL002 during the Core Study. They will continue at their Core Study AL002 dosage during the LTE Study if enrolled in the LTE Study. Group T-T is further broken down as AL002 15 mg/kg, 40 mg/kg, and 60 mg/kg treatment groups.

- **Group P-TC** includes participants who were exposed only to placebo during the Core Study. They will be assigned to the TC during the LTE Study if enrolled in the LTE Study. Group P-TC might be separated into placebo and TC treatment groups depending on the summaries/analyses.

For Group P-TC, the data collected when the participants were receiving placebo in the Core Study might be summarized and/or analyzed separately from the data collected once the participants received the first study drug administration in the LTE Study. The data collected when the participants were receiving placebo in the Core Study up to the day before the participants received the first study drug administration in the LTE Study (separately from the data collected in the LTE Study) is referred to as **the Placebo Data** throughout the SAP. And it includes the data from the placebo participants who did not enroll in the LTE Study. The data collected on or after the day when the participants received the first study drug administration in the LTE Study is referred to as **the TC Data** throughout the SAP.

The first dose date of AL002 refers to the earliest date of any amount of AL002 administered across the Core Study and the LTE Study. **The last dose date of AL002** refers to the latest date of any amount of AL002 administered across the Core Study and the LTE Study. **The first dose date of any study drug** refers to the earliest date of any study drug administered, including placebo, across the Core Study and the LTE Study.

3.3 Randomization

Not applicable. Participants are categorized per their assigned treatment groups in the Core Study.

3.4 Hypothesis Testing

There are two hypotheses to be tested. First there is the efficacy null hypothesis of the core study: The null and alternate hypotheses for comparing each of the treatment groups to placebo are as follows:

H_0 (null): $\theta \leq 0$, indicating that treatment does not slow disease progression relative to placebo control,

H_1 (alternative): $\theta > 0$, indicating that treatment slows disease progression relative to placebo control,

where θ represents the treatment effect, defined as a proportional reduction of the placebo group clinical decline in the CDR-SB.

Secondly, there is a test of the null hypothesis that dose titration speed has no effect on occurrence of first ARIA events. The null and alternate hypotheses for comparing treatment with slower titration against treatment with faster titration are:

H_0 (null): $\tau = 0$, indicating that slower titration does not change first ARIA event incidence relative to treatment with faster titration,

H_1 (alternative): $\tau \neq 0$, indicating that slower titration changes first ARIA event incidence relative to treatment with faster titration,

where τ represents the slower titration effect, defined as difference in first ARIA event incidence relative to the group with faster titration.

3.5 Sample Size

It is expected that 80% to 90% of the participants who completed the planned treatment period in the Core Study and are not APOE e4/e4 will enroll in the LTE Study. Currently, there are 220 such participants in the Core Study who either completed planned treatment or are ongoing, so 176 to 198 participants are expected.

4. DATA AND ANALYTICAL QUALITY ASSURANCE

The overall quality assurance procedures for the study data, statistical programming and analyses are described in Everest's Standard Operating Procedures. Detailed statistical and programming quality control (QC) and quality assurance (QA) procedures are documented in the Statistical Analysis and Programming QC/QA Plan.

The study endpoints and analytic approaches are both prospectively defined and documented in the protocol and in this SAP. The SAP will be finalized prior to the Core Study database lock.

5. ANALYSIS SETS

When change (or percent change) from baseline is assessed, participants will be included in applicable analysis sets and in the analysis only if the participants had both a baseline and a postbaseline measure.

5.1 As-Treated Set (ATS)

The ATS is the same as the ATS of the Core Study and consists of all participants who received any amount of study drug administration in the Core Study.

All analyses using the ATS will group participants according to the highest dose level of AL002 received as determined in the Core Study (i.e., AL002 15 mg/kg, 40 mg/kg, or 60 mg/kg), except for Group P-TC. Participants in Group P-TC will remain in Group P-TC regardless of the highest dose level received, but they will be presented as two groups: Placebo (for data during placebo treatment) and Titration Cohort (for data during LTE titration). This grouping is referred to as actual treatment.

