3. STUDY DESIGN

3.1 Study Design

This is a Phase 2, LTE study of participants with AD. The study will enroll participants who completed the planned treatment period in AL002-2 (Core Study). Study sites are located in North America, Australia, Europe, and Argentina.

Participants who were randomized to active treatment in the Core Study will remain on their previously assigned dose. Participants who were previously on placebo in the Core Study will be assigned to the Titration Cohort (TC), which will initiate with a starting dose of either 2 mg/kg or 6 mg/kg that will be increased over 32 weeks or 24 weeks, respectively, to reach the target dose of 60 mg/kg per the Titration Algorithm (for details of the Titration Algorithm, refer to the Study Protocol).

The planned duration of the LTE study is 56 weeks, and LTE study treatment extends from LTE Day 1 to Week 48. Dosing duration may be extended beyond this time through a protocol amendment, within the context of emerging favorable safety data. AL002 will be administered via IV infusion at the study site on Day 1 (after all necessary baseline assessments have been completed) and will be repeated subsequently once every 4 weeks throughout the treatment period.

The first dose of the AL002-LTE should be within the 4-week window (± 5 days) of the last dose of the Core Study, to maintain continuity of study treatment. Delays of the first AL002-LTE dose beyond that window will constitute protocol deviations.

Dosing for any individual participant may be stopped, paused, or reduced based on emerging safety data and/or the development of ARIA-E or ARIA-H. If a participant discontinues the study prior to the end of their planned treatment period, they will need to return for an Early Termination (ET) Visit and that will mark the end of their participation in the study.

At study entry and throughout the treatment period, safety will be assessed through monitoring of AEs (including AESIs and SAEs), changes in laboratory and vital sign values, incidence of findings from physical, neurological, ECG, MRI, ophthalmological exams, and reports of suicidal ideation or behavior. Serum PK will be assessed for investigation of exposure-response and exposure-safety relationships. Blood samples for assessment of ADA will be taken throughout the study.

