5.2 Analysis Sets Excluding APOE e4-homozygous (e4/e4) Participants

5.2.1 Non-e4/e4 Set

The Non-e4/e4 Set is the same as the Non-e4/e4 Set of the Core Study and consists of all participants who received any amount of study drug administration in the Core Study and who are not APOE e4/e4 (i.e., non-e4/e4).

All analyses using the Non-e4/e4 Set will group participants as described above for the ATS.

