7.4 Safety Analyses

All safety endpoints will be summarized with the Integrated Analysis, unless otherwise specified. The selected safety endpoints that will be summarized with the LTE Analysis are specified in the respective sections.

All LTE Analysis for a safety endpoint will be based on the ATS-LTE, unless otherwise specified. All Integrated Analysis for a safety endpoint will be based on the Non-e4/e4 Set, unless otherwise specified. Analysis sets are defined in Section 5.

Analyses (including analysis sets that analyses will be conducted on) to be performed for each interim analysis (IA) are specified in Section 8.

Unless otherwise specified, CFB for Group T-T and placebo will be based on the Core baseline. CFB for Titration Cohort will be based on the LTE baseline. Baseline is defined in Section 6.1. Core baseline and LTE baseline are referred to as baseline for simplicity in this section.

Analysis visit window definitions are described in Section 7.1.1.2.1.

In the case of multiple values in an analysis visit window, data will be selected for analysis as described in Section 7.1.3.2, unless otherwise specified.

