All of the MRI summaries described above will also be provided separately for participants with the following APOE genotype(s) (1) e4 carriers (including e2/e4, e3/e4 and e4/e4), and (2) non-e4 carriers (excluding e2/e4, e3/e4 and e4/e4).

For Integrated Analysis, all summaries described in this section will be provided for events across two studies as defined in Section 7.4.1.2. For LTE Analysis, only the overall summary of ARIA will be provided for events during the LTE Study.

For Integrated Analysis, the difference in proportion of participants with ARIA-E events between a slower titration rate over 48 weeks and a faster titration rate over 48 weeks will be estimated by the Cochran-Mantel-Haenszel (CMH) method adjusting for the APOE e4 status. The faster titration rate will be represented by data from the AL002 60 mg/kg treatment group during the first 48 weeks of the Core Study among participants who were on dose titration (i.e., received the first dose on or after July 22, 2021 in the Core Study) and had at least one evaluable post-baseline MRI scan. The slower titration rate will be represented by data from the first 48 weeks of the LTE Study, among Titration Cohort participants who had at least one evaluable post-baseline MRI scan in the LTE Study. Both 90% and 95% CIs for the difference in the ARIA-E events and p-value will be reported from the CMH method. The same analysis will be repeated for ARIA-H.

The statistical tests (the CMH method) of ARIA events between the slower and faster titration groups will not be performed at the first IA at the time of unblinding of the Core Study due to limited data from the LTE study at this IA, but will be performed in all analyses after the first IA.

In the Integrated Analysis, the Kaplan-Meier curves for the time to the first occurrence of ARIA-E during both the Core and LTE Studies will be plotted. For participants who experienced at least one ARIA-E, the time to the first occurrence of ARIA-E is the time from the first dose date to the onset date of the first ARIA-E occurrence. For participants who did not experience ARIA-E, the censor date will be the earlier date of the last MRI scan date, any death date, and the last dose date plus 90 days. Similarly, the Kaplan-Meier curves for the time to the first occurrence of ARIA-H will be plotted.

All MRI findings will be listed.

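### SAP 5.1 and 3.3 conflict on who forms the fast arm of the ARIA titration tests; under 5.1, dose reached decides membership in that arm only

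*SAP*

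**What the plan says.** SAP 7.4.8 compares the proportion with ARIA-E under slow and fast titration by a Cochran-Mantel-Haenszel (CMH) analysis adjusted for APOE e4 status. The fast arm is "represented by data from the AL002 60 mg/kg treatment group during the first 48 weeks of the Core Study", limited to those first dosed on or after 22 July 2021 with an evaluable post-baseline MRI. The slow arm is the first 48 weeks of the LTE "among Titration Cohort participants who had at least one evaluable post-baseline MRI scan in the LTE Study". For the second finding: "The same analysis will be repeated for ARIA-H".

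Section 7.4.8 states no analysis set for these tests. Four other places bear on who is in each arm:

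- SAP 7.4: "All Integrated Analysis for a safety endpoint will be based on the Non-e4/e4 Set, unless otherwise specified".
- SAP 5.2.1: "All analyses using the Non-e4/e4 Set will group participants as described above for the ATS".
- SAP 5.1: analyses on the As-Treated Set (ATS) "group participants according to the highest dose level of AL002 received as determined in the Core Study". The placebo-origin group is exempt: "Participants in Group P-TC will remain in Group P-TC regardless of the highest dose level received".
- SAP 3.3, in place of a randomisation scheme, says that participants are sorted by the treatment assigned to them in the Core Study.

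**The concern.** The hypothesis in SAP 3.4 is about titration speed. A person who stops during titration has experienced that titration and belongs in the comparison, whichever arm they are in.

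Followed through 7.4, 5.2.1 and 5.1, the SAP keeps such a person in the slow arm. In the fast arm it appears to remove them, because they never received 60 mg/kg. Membership would then depend on dose reached, a post-baseline result that ARIA can influence, in one arm only. SAP 3.3 points the other way, so two programmers could build different fast arms from the same plan.

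At stake is the inference on a primary objective, the effect of titration on ARIA. The two CMH tests in 7.4.8 are its only planned inferential tests.

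**Working it through.** **1. Where the tests land.** Section 7.4.8 places the comparison under the Integrated Analysis and names no set. SAP 7.4 then supplies the Non-e4/e4 Set, and SAP 8.1.3 names the same set for the 7.4.8 ARIA summaries at the interim. SAP 5.2.1 carries over the ATS grouping, and SAP 5.1 groups by highest dose received with the Titration Cohort exempt. The Full Analysis Set (SAP 5.2.3) groups by assigned dose, but 7.4.8 does not call on it. SAP 3.3 gives assigned dose as the general rule. Section 5.1 is the more specific text, but nothing says that it overrides 3.3.

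**2. Who could be moved.** Protocol 1.2.2 says that the Core 60 mg/kg arm was titrated over 3 doses, given every 4 weeks. The step doses are not stated. If the third dose is the first at 60 mg/kg (an inference), it falls on Day 1 + 2 × 28 = Day 57.

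SAP Table 7-12 puts the Core MRI target days through Week 48 at 15, 29, 43, 57, 85, 169 and 337. Four of the seven are on or before Day 57, so a participant can have evaluable scans and still stop before 60 mg/kg. In the slow arm, SAP 3.1 has a starting dose "that will be increased over 32 weeks or 24 weeks, respectively, to reach the target dose of 60 mg/kg". Stopping at any point in that period leaves the participant in the slow arm.

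**3. Size.** The arm sizes and ARIA-E rates in Protocol 8.1 are redacted. The one sample size that can be checked is in SAP 3.5: 0.80 × 220 = 176 and 0.90 × 220 = 198, as stated. Split equally over four arms (an assumption), that is 44 to 49.5 per arm.

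The rest is illustration on assumed inputs: 50 randomised to 60 mg/kg and a slow-arm rate of 10%. Let *p* be the fast-arm rate among all randomised, *c* the ARIA-E cases and *m* the non-cases who never reach 60 mg/kg. Then

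observed fast-arm rate = (50*p* − *c*) / (50 − *c* − *m*).

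Power is two-sided at 5%, from the pooled-variance normal approximation without stratification.

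| *p* | *c*, *m* | Observed rate | Power, slow n = 50 | Power, slow n = 44 |
|---|---|---|---|---|
| 0.30 | 0, 0 | 15/50 = 30.0% | 71% | 68% |
| 0.30 | 1, 0 | 14/49 = 28.6% | 65% | 62% |
| 0.30 | 2, 0 | 13/48 = 27.1% | 59% | 55% |
| 0.30 | 0, 1 | 15/49 = 30.6% | 73% | 69% |
| 0.30 | 0, 2 | 15/48 = 31.3% | 75% | 71% |
| 0.30 | 1, 1 | 14/48 = 29.2% | 67% | 64% |
| 0.20 | 0, 0 | 10/50 = 20.0% | 29% | 26% |
| 0.20 | 2, 0 | 8/48 = 16.7% | 16% | 15% |
| 0.20 | 0, 2 | 10/48 = 20.8% | 32% | 29% |

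The rate is understated if ARIA cases stop before 60 mg/kg more often than others, unchanged if equally often, and overstated if less often.

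**The case against.** The case on the other side has four parts.

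- **The SAP may already intend assigned dose.** Section 3.3 says so in general terms, and 3.2 describes the 15, 40 and 60 mg/kg groups without a highest-dose rule. This stands far enough to make the matter a conflict in the text and not a settled exclusion.
- **The deciding rule may lie elsewhere.** Section 5.1 defers to how dose level was determined in the Core Study, and the Core SAP is not supplied. If that plan classes early stoppers by assigned dose, nobody moves. This stands, and so does the caution that Day 57 is inferred.
- **The route out is narrow.** The participant must be non-e4/e4, have an evaluable scan, and stop permanently before the first 60 mg/kg dose. Under Protocol Table 8, a first non-serious ARIA-E of any grade suspends dosing, with possible resumption and further up-titration. Protocol 5.1 says that LTE management is consistent with the parent study. Some ARIA-H findings do end treatment, so a route remains, chiefly for the ARIA-H test. The count of four MRI visits in seven shows opportunity to be scanned, not people lost.
- **As-treated grouping is normal for safety.** That is true of the general tables. It does not justify different membership rules in the two arms of one test.

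A reader might infer that the plan hides ARIA cases from the fast arm, or that power is seriously reduced. The documents support neither. Protocol 1.2.2 and 1.3 place the serious and severe symptomatic cases in e4/e4 participants, whom this set excludes. No document gives the share of cases that stopped early. If cases do leave, the fast-arm rate falls, which counts against slow titration and does not create a false benefit.

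**Conclusion.** The point holds as a minor one. The SAP gives two answers on who is in the fast arm. The answer reached through its analysis-set rules applies a post-baseline condition to that arm alone, in both CMH tests.

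The effect of that answer rests on two things that the documents do not settle: the Core SAP's rule for dose level, and 60 mg/kg being first given at the third dose. Its direction and size cannot be derived, and the number affected is probably small. In the illustration, up to two cases or two non-cases lost moves a 30% rate by −2.9 to +1.3 points, and a 20% rate by −3.3 to +0.8 points. These ranges span zero. They depend on an assumed arm size, assumed rates and an assumed number of leavers, and the power figures ignore the planned stratification.

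**What to change.** In SAP 7.4.8, define the fast arm for both the ARIA-E and the ARIA-H test as all non-e4/e4 participants randomised to 60 mg/kg in the Core Study, first dosed on or after 22 July 2021, with at least one evaluable post-baseline MRI, whatever dose level they reached. State there which of SAP 3.3 and 5.1 governs these tests. Keep grouping by highest dose received as a sensitivity analysis, and report how many participants differ between the two definitions. Leave the general by-dose safety tables as treated.

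The cost is a sentence or two, and assigned dose is already in use for the Full Analysis Set. The fast-arm count may differ from the 60 mg/kg column of the as-treated tables, which a footnote can explain. If the Core SAP already uses assigned dose, the change only makes that explicit.

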5.2 Analysis Sets Excluding APOE e4-homozygous (e4/e4) Participants

5.2.1 Non-e4/e4 Set

The Non-e4/e4 Set is the same as the Non-e4/e4 Set of the Core Study and consists of all participants who received any amount of study drug administration in the Core Study and who are not APOE e4/e4 (i.e., non-e4/e4).

All analyses using the Non-e4/e4 Set will group participants as described above for the ATS.

5.2.2 As-Treated Set – LTE (ATS-LTE)

The ATS-LTE consists of all participants who received any amount of study drug administration in the LTE Study. No e4/e4 participants were enrolled in the LTE Study.

All analyses using the ATS-LTE will group participants as described above for the ATS.

5.2.3 Full Analysis Set (FAS)

The FAS is the same as the FAS of the Core Study and consists of all participants who were randomly assigned in the Core Study, received any amount of study drug, and are non-e4/e4.

A participant's status of APOE e4 and APOE genotype will be determined by the APOE genotype central laboratory data provided by the vendor in the Core Study. If a participant's APOE genotype is not e4/e4, then the participant is not APOE e4-homozygous (i.e., the participant is a non-e4/e4 participant). In other words, the FAS excludes e4/e4 participants.

All analyses using the FAS will group participants either to the assigned treatment in the Core Study (i.e., AL002 15 mg/kg, 40 mg/kg, or 60 mg/kg) or to Group P-TC, but they will be presented as two groups: Placebo/TC (for analyses using Core Study Baseline) and Titration Cohort (for data during LTE titration using LTE Study Baseline).

5.2.4 Pharmacokinetic Set (PKS)

The Pharmacokinetic Set will include all participants in the ATS that received AL002, had at least one post-dose measurable concentration, and are non-e4/e4.

All analyses using the PKS will group participants as described above for the ATS.

6. SPECIFICATION OF ENDPOINTS AND VARIABLES

6.1 Demographics and Baseline Characteristics

The Core baseline is the baseline defined and used in the Core Study (refer to the AL002-2 SAP for details).

Selection of the LTE baseline is specified in Section 7.1.2.

The **last participation date** is the date of last visit (any scheduled, unscheduled, EOS, ET, EFU, or SFU visit) or AE assessment during the study.

6.1.1 Demographics and Baseline Characteristics

Demographic information, including year of birth, age at time of informed consent (in years), sex, race, ethnicity and handedness are collected at the Screening visit of the Core Study and might be updated during the Screening period of the LTE Study.

Weight and height are collected at the Screening visit for the Core Study and might be updated during the Screening period of the LTE Study, if not collected at the final visit of the Core Study. Weight will be collected throughout the LTE Study. Body mass index (BMI) will be calculated as the weight in kg divided by the square of height in meters.

Age at AD diagnosis will be calculated from the date of diagnosis and birth year as $\{(year\ of\ diagnosis) - (year\ of\ birth)\}$ as collected at the Screening visit of the Core Study and will not be updated for the LTE Study.

Time since AD diagnosis will be calculated from the date of diagnosis and informed consent date as $\{(informed\ consent\ date) - (AD\ diagnosis\ date) / 365.25\}$ and will be updated for the Titration Cohort as being based on LTE informed consent date. If AD diagnosis date is partially missing, unknown day will be imputed as the 1st, and unknown month will be imputed as January.

The countries where a participant is enrolled in the Core Study at will be grouped into geographical region, namely, United States and rest of the world.

A participant's APOE e4 status and APOE genotype will be determined by the APOE genotype central laboratory data provided by the vendor in the Core Study. If a participant's APOE genotype contains "e4", the participant is considered an e4 carrier (or carrier); otherwise, a non-carrier.

The PD biomarker assessments will consist of blood-based biomarkers, CSF-based biomarkers (optional sub-study), and imaging biomarkers (MRI efficacy, sub-studies of amyloid PET, and Tau PET) and will

be collected during screening or pre-dose of the Core Study and the LTE Study. Other timing and frequency of all PD biomarker assessments are presented in the Schedules of Assessments in protocols.

Demographic variables will include the following:

- Age (years) at time of informed consent in the LTE Study as a continuous variable and as categories
 - Age group 1
 - < 65 years
 - ≥ 65 years
 - Missing (including blank, not reported, unknown, etc.)
 - Age group 2
 - < 65 years
 - ≥ 65 – < 75 years
 - ≥ 75 years
 - Missing (including blank, not reported, unknown, etc.)
- Sex
 - Female
 - Male
 - Missing (including blank, not reported, unknown, etc.)
- Race
 - American Indian or Alaska Native
 - Asian
 - Black or African American
 - Native Hawaiian or Other Pacific Islander
 - White
 - Multiple
 - Missing (including blank, not reported, unknown, etc.)
- Ethnicity
 - Hispanic or Latino
 - Not Hispanic or Latino
 - Missing (including blank, not reported, unknown, etc.)
- Handedness
 - Always Right
 - Usually Right
 - Either Hand
 - Usually Left
 - Always Left
 - Missing (including blank, not reported, unknown, etc.)
- Weight (kg)
- Height (cm)
- BMI (kg/m²) as a continuous variable and as categories
 - < 18.5 kg/m²
 - 18.5 – < 25.0 kg/m²
 - 25.0 – < 30.0 kg/m²
 - ≥ 30.0 kg/m²

- Geographical region
 - United States
 - Rest of World

Baseline disease characteristics and baseline COAs will include the following:

- Age at AD diagnosis (years)
- Time since AD diagnosis (years)
- APOE e4 status
 - Carrier
 - Non-carrier
 - Missing (including blank, not reported, unknown, etc.)
- APOE genotype
 - e2/e3
 - e2/e4
 - e3/e3
 - e3/e4
 - Missing (including blank, not reported, unknown, etc.)
- AD diagnosis
 - Mild Cognitive Impairment (MCI) due to Alzheimer's disease
 - Mild Dementia due to Alzheimer's disease
- Baseline clinical dementia rating – global score (CDR-GS) as a continuous variable and as categories
 - 0.5
 - 1
 - Missing (including blank, not reported, unknown, etc.)
- Baseline CDR-SB
- Baseline MMSE
- Baseline RBANS
- Baseline ADAS-Cog13
- Baseline ADCS-ADL-MCI score
- Baseline ADCOMS
- Baseline modified iADRS

